For those determined to be eligible, the following will occur:

- Complete medical history and physical exam
- Baseline Blood Tests including:
 - TPN panel
 - Liver profile
 - Renal profile

- Ca
- P04
- Mg
- Triglycerides
 - Essential fatty acid levels
 - Thromboelastography (TEG) - with platelet mapping preferred
 - CBC, differential, platelets.
 - PT/PTT (at outset and then monthly)
 - Cholesterol
- Pregnancy test (urine) for females of child-bearing potential.

All patients will be followed as inpatients within the Regional Center for Neonatal Care (RCNC), the Department of Surgery, and the Division of Gastroenterology. As outpatients they will be followed within the Comprehensive Nutrition Clinic (CNC). Laboratory monitoring of patients with intestinal failure on TPN can be found on Compliance 360. Inpatients undergo the same monitoring, but a TPN panel and CBC are performed once weekly. Outpatients will undergo weekly monitoring of vital signs and fluid balance as well as inspection of gastrostomies, enterostomies, and central venous catheter exit sites by home healthcare nurses.

While they are on Omegaven® they will be seen and examined twice a month for study visits, and they will undergo blood sampling twice a month to obtain repeat levels of their baseline tests for the first 6 months. After the first 6 months, they will be seen and examined monthly and will undergo monthly blood sampling. Adverse events and concomitant medication information will be collected and documented at each study visit.

Below is a description of the study procedures:

Medical History and Physical

A complete, comprehensive history and physical will be performed at the beginning and end of the study. An interim medical history and a brief physical exam will be performed at all other study visits.

Clinical and demographic data will also be obtained to include: age, gender, race, and current medications.

At other study visits, an abbreviated physical exam will be performed and changes in medical history or concomitant medications will be noted.

Phone Calls:

For the first 6 months of the study, a study coordinator will contact research participants/families weekly to assess for any changes in health status and changes to medications. Thereafter, the coordinator will contact participants/ families monthly

approximately midway between monthly clinic visits. Changes in clinical status and concomitant medications will be monitored until the end of the study.

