Following completion of the study medication, subjects will be seen for a final study visit within 1 month for a follow-up assessment. A complete, comprehensive history and physical will be performed. Blood samples will be collected and a urine pregnancy test will be done for females of childbearing potential. Adverse events and concomitant medications will be documented by the study staff.

The following table summarizes Study Procedures:

Study Procedures Table

	Baseline (Day 0)	Weekly while Inpatient	Weekly for first 6 months	Twice a month for the first 6 months	Monthly	Final Visit (within 1 month after treatment)
Signed informed consent/assent	X					
History	X			X	X	X
Physical Exam	X	X		X	X	X
Blood specimen (4.4 mcl using microtainers) [#]	X	X		X	X	X
Urine pregnancy test*	X				X	X
Phone calls (clinical status and concomitant medication collection)			X		X **	

At baseline and then monthly for PT/PTT. At baseline and then weekly for other laboratory studies (see Section IX, E).

* For females of child-bearing potential.

** Phone calls will take place monthly (between the monthly visits)

G. Data Collection

Demographic and clinical information will be collected whenever clinical data are available via uniform baseline and follow up clinical data extraction forms to ensure accuracy and consistency. The essential demographic information includes age at diagnosis, gender, race and ethnicity, birth history, past medical history, and family history. The clinical information includes presence or absence of jaundice, hepatosplenomegaly, or ascites.

H. Compensation

Participants will not be compensated for study participation. Subjects will receive study medication, clinical supplies, and laboratory evaluations that are obtained outside the standard of care free of charge.

I. Withdrawal

Protocol – Compassionate Use of a Fish Oil-derived Intravenous Fat Emulsion (Omegaven[®]) to Reverse Parenteral Nutrition (PN) Induced Cholestasis

Data collected from patients who withdraw from the study will be included in the final analysis using intent to treat. Patient enrollment will continue until all 25 patients complete all requested study requirements outlined. It will be recommended that patients withdrawn from the protocol resume a reduced lipid intake, treat infections promptly as they occur and advance feedings as quickly as tolerated.

X. Assessment of Efficacy

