The primary endpoint will be reduction in conjugated or direct bilirubin level to below 1 mg/dl. Data from previous retrospective analyses and prospective uncontrolled studies suggest that from the inception of Omegaven® therapy, conjugated or direct bilirubin will remain elevated for approximately 8 weeks at levels comparable to those observed prior to administration of Omegaven®. Subsequently, levels are expected to fall by approximately 1 mg/dl/week until they normalize. The time to normalization will vary according to each patient's baseline conjugated or direct bilirubin level. Thus, a patient who begins Omegaven® with a conjugated or direct bilirubin level of 7 mg/dl is likely to experience normalization within 14 weeks (8+6 weeks). We will compare the group receiving Omegaven® with historical controls from our internal registry who have demonstrated cholestasis while on Intralipid®. We will compare changes in conjugated/direct bilirubin concentration over time between groups via Kaplan-Meier analysis (see Statistics section XIII).

Secondary endpoints will be: normalization of total bilirubin and liver enzymes. Differences in these values at the end of 14 weeks of therapy will be compared with those of controls via Kaplan-Meier analysis identical to that employed for conjugated and direct bilirubin levels. Furthermore, we expect that elevated triglyceride levels which might be present at the initiation of therapy will have normalized at the same time that liver profiles have normalized.

XI. Assessment of Safety/Data Safety Monitoring Board

A DSMB will monitor the study for the occurrence of adverse events (both serious and otherwise). A significant increase in the rate of adverse events would be cause for concern for the safety of participants in the study. Information on adverse events will be presented in several ways: (1) listings of serious adverse events with accompanying narrative summary by the PI; (2) summaries of adverse events by body system and type of event. This information will be presented to the DSMB.

The DSMB will also monitor the efficacy and the conduct of the study. Interim monitoring reports for the DSMB will include, but will not be limited to, such tabulations as:

1. platelet counts
2. essential fatty acid profiles
3. coagulation studies
4. liver profiles

5. renal profiles

The DSMB will meet at least once per year and possibly more frequently given the expected speed of recruitment and study medication administration.

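### The primary comparison with registry controls has no common bilirubin assessment schedule and one value below 1 mg/dl counts as success, so any difference in sampling frequency would bias it

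*Combined protocol and SAP*

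**What the plan says.** Section X sets the endpoint: "The primary endpoint will be reduction in conjugated or direct bilirubin level to below 1 mg/dl". It asks for no repeat value and no duration. By contrast, inclusion criterion 3 asks for 3 mg/dl or more over more than 4 weeks.

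The treated schedule is in IX.F. While on drug, "they will undergo blood sampling twice a month to obtain repeat levels of their baseline tests for the first 6 months"; the baseline tests include a liver profile. Later, "After the first 6 months, they will be seen and examined monthly and will undergo monthly blood sampling". On ward monitoring it adds: "Inpatients undergo the same monitoring, but a TPN panel and CBC are performed once weekly". The footnote to the Study Procedures Table reads "At baseline and then weekly for other laboratory studies", with PT/PTT as the monthly exception.

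For the comparator, section X says "We will compare the group receiving Omegaven® with historical controls from our internal registry". Section XIII names Kaplan-Meier and Cox models. Neither section gives a control sampling interval, a visit window, a common grid or a method for interval-censored times. No follow-up cut-off is set for the primary endpoint: section X attaches 14 weeks to the secondary endpoints, and the sample size uses 8 weeks.

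**The concern.** Bilirubin is seen only on sampling days, so the recorded event time is the first sample after the true crossing. A group sampled more often has real normalization dated earlier. It also has more chances for a brief dip to count, because one value is enough. An ordinary Kaplan-Meier or Cox analysis reads both effects as a treatment difference. With a fixed treated schedule and registry controls on an unstated one, the primary result could partly reflect how often each group was tested. A single dip is also weak evidence that cholestasis has been reversed, which is the stated aim.

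**Working it through.** **1. The plan's own figure.** Section XIII: 10% versus 50% resolved within 8 weeks, alpha 0.05 (two-sided assumed), power 0.80 (the text's beta of 0.80 read as power), 19 per group.

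n = [1.96√(2·0.30·0.70) + 0.842√(0.10·0.90 + 0.50·0.50)]² / 0.40² = (1.270 + 0.491)² / 0.16 = 19.4, so 20. The arcsine formula gives 18.3, so 19. The figure reproduces. It makes no allowance for unequal assessment.

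**2. Detection delay.** With sampling every d weeks, the mean delay after the true crossing is about d/2: 1 week for 2-weekly, 2 weeks for 4-weekly and 4 weeks for 8-weekly sampling. On section X's expected course (flat for 8 weeks, then down 1 mg/dl a week), a child starting at 6 mg/dl reaches 1 mg/dl at week 8 + 5 = 13. Samples at weeks 2, 4, … detect this at week 14; samples at weeks 4, 8, … detect it at week 16. With a 14-week cut-off, the same child is an event on one schedule and censored on the other.

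**3. Transient dips.** With independent normal values, p = Φ((1 − μ)/σ) and P(at least one below 1) = 1 − (1 − p)ⁿ. Over 14 weeks, n is 14, 7 or 3 for weekly, 2-weekly or 4-weekly sampling. The means and SDs are assumptions.

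| Child's mean, SD (mg/dl) | p | Weekly | 2-weekly | 4-weekly |
|---|---|---|---|---|
| 1.5, 0.4 | 0.106 | 79% | 54% | 28% |
| 3.0, 0.8 (same CV) | 0.0062 | 8% | 4% | 2% |

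Dips matter for a child hovering just above the threshold and little for one who stays at the entry level.

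**4. Effect on the test.** Simulation of 25 versus 25 children with the same true course in both groups, treated children sampled every 2 weeks, a single value below 1 mg/dl, and a log-rank test (1,000 runs per case). Assumptions: 25 controls, baseline median 6 mg/dl, within-child CV 20% or 40%, follow-up 14 or 26 weeks, and the control intervals. Entries are the chance of a significant result favouring Omegaven (nominal 2.5%; simulation standard error about 0.5 points at that level).

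| Controls sampled | Section X course | Only 25% resolve | Plateau at 0.8 to 4 mg/dl |
|---|---|---|---|
| Weekly | 0.6–0.9% | 1.7–2.9% | 0.5–1.8% |
| Every 2 weeks | 1.5–2.8% | 1.9–2.8% | 2.0–2.6% |
| Every 4 weeks | 16–21% | 2–4% | 4–10% |
| Every 8 weeks | 71–73% | 4–8% | 7–23% |

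On the section X course at 14 weeks, the share reaching the endpoint is 63%, 57%, 43% and 22–23% with sampling every 1, 2, 4 and 8 weeks. By 26 weeks it is 99%, 99%, 98% and 96%, and the difference is almost all in mean detected time: 14.1, 14.6, 15.5–15.6 and 17.3–17.4 weeks. Other simulation settings gave 38% and 51% false positives at 14 weeks with 4-weekly controls, so 21% is not an upper limit.

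**5. Confirmation on unequal schedules.** On the section X course with 4-weekly controls, requiring two consecutive values and dating the event at the second raised false positives from 20–21% to 87–88% at 14 weeks and from 16–17% to 73% at 26 weeks. A separate run with other settings gave 36% with confirmation against 38% without at 14 weeks, and 25% against 21% at 26 weeks. In no case was the bias removed. With both groups on a 2-week grid, the confirmed endpoint gave 2.3–2.7%.

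Confirmation also needs follow-up. With 4-weekly sampling, only 1–2% of children have a confirmed event by 14 weeks, against 94% by 26 weeks.

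**The case against.** The strongest objection is that unequal sampling is nowhere stated. Sections IX.D and IX.F tie blood tests to the institution's standards for children on TPN, and the weekly inpatient panel is described alongside that routine monitoring. Controls come from the same institution's registry and may have been tested just as often. This stands. A reader might infer that controls were looked at less often and that the comparison therefore favours Omegaven; the documents do not support that. Some text points the other way: IX.H says the study pays for tests beyond standard care, which suggests extra sampling, but it does not say which tests. The institutional monitoring document is not supplied and parts of the protocol were withheld from the text, so a control schedule may exist elsewhere.

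It is also fair to say that the dip figures for a child at 1.5 mg/dl are a worst case, that the large false-positive rates need most children in both groups to resolve, and that a one-week mean delay is small beside a planned contrast of 10% versus 50%. All this limits the size. It does not supply the missing alignment rule, and the plan cannot show that the bias is absent.

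**Conclusion.** The gap is real: a single value suffices, the treated schedule is fixed, and no common schedule or interval-censored method governs the comparison with controls. Whether this produces bias, and in which direction, depends on a control sampling interval that the documents do not give. Less frequent control sampling would favour Omegaven; equal sampling leaves the error rate at its nominal level; weekly sampling would remove the bias or turn it against Omegaven.

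Under the assumed 4-weekly control interval and identical true courses, false positives run from about nominal (few children resolving) to well above 15% (section X course). The size also depends on the follow-up cut-off, which is not set for this endpoint. These figures rest on assumed baseline levels, variability and control numbers. They show what is possible; they do not estimate the bias in this trial.

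**What to change.** 1. Before outcomes are compared, tabulate the bilirubin sampling intervals of the registry controls alongside those of the treated children.
2. In sections X and XIII, run the primary comparison with both groups reduced to one assessment grid, spaced at the sparser group's interval and counted from a stated starting point in each group. Alternatively, use an interval-censored time-to-event analysis. State the follow-up cut-off.
3. Only on that common grid, and only with follow-up long enough to supply a second value, count an event when two consecutive values are below 1 mg/dl, dated at the first, under the same rule in both groups. The final visit in IX.F should not serve as the confirming value, since only treated children have it. Keep the single-value result as a sensitivity analysis.
4. Do not apply a confirmation rule while schedules differ.

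The cost is protocol wording, one tabulation and some programming, with no new visits or samples for treated children. Event times become coarser and slightly fewer events are counted if follow-up is adequate. With a short cut-off the loss from confirmation would be large, as the 14-week figures in step 5 show.

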body weight per day, and who are unlikely to tolerate substantial enteral nutrition until several months following their small intestinal insult.

II. Purpose of Study

The specific aim of this study is to ascertain whether PNAC can be reversed if a fish oil-based intravenous lipid product (Omegaven®) at a dose of up to 1 g/kg body weight/day is substituted for a soy-based intravenous lipid product (Liposyn® or Intralipid®) as part of the daily TPN of infants and children with intestinal failure and PNAC. Secondary aims will be to confirm the safety of Omegaven®.

III. Background

In North America, infants and children who require parenteral nutrition (TPN) customarily receive solutions whose caloric distribution is balanced between glucose, protein, and fat to provide approximately 60-70 % of calories via glucose, 10-15 % of calories via protein, and 20-30% of calories via lipid.(1) Commercial lipid solutions utilized in North America are customarily soy-based, and contain high quantities of phytosterols including sitosterol and stigmasterol. Animal data suggest that high quantities of stigmasterol inhibit fxr, a nuclear receptor in the hepatocyte that helps to regulate bile acid homeostasis by controlling expression of bile acid export pumps. (2) Thus, exposure to a high quantity of stigmasterol is potentially hepatotoxic to individuals who have a propensity for cholestasis due to a poorly developed bile secretory process.

It is known that infants and children with underlying intestinal failure are at extraordinarily high risk for cholestasis. (3) The cholestatic process is reversible in approximately ¼ of infants with parenteral nutrition associated cholestasis (PNAC), even when soy-based lipid emulsions are given parenterally, if those infants can experience small intestinal adaptation and ultimately tolerate and assimilate the majority of their calories via enteral nutrition. Unfortunately, if adaptation does not occur rapidly enough, PNAC may progress to endstage liver disease resulting in death or necessitating combined liver/small intestinal transplantation.

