A popular strategy for minimizing the toxicity of lipid emulsions is to reduce the amount of lipid in parenteral nutrition to between 0.5 g/kg body weight/day and 1g/kg body weight/day. (4) Preliminary results suggest that this strategy is beneficial for some infants, but that it is not universally effective. One potential reason for lack of effectiveness among some cholestatic infants is that endotoxemia is commonplace in children with intestinal failure receiving TPN, and that stigmasterol potentiates the cholestatic effect of endotoxin upon the liver. Therefore, when the infant with a cholestatic propensity is exposed to endotoxin and even modest quantities of stigmasterol, cholestasis could progress.

An alternative liver-protective strategy for children on TPN has been to provide all of the patients' parenteral lipid in the form of a fish-oil based product called Omegaven®. (5) This product has been used for over 10 years as an adjunct to conventional fat emulsions.

According to current data, an increase in the proportion of omega-3 fatty acids is thought to optimize nutrition in general, but in particular benefit patients whose underlying disease might benefit from an increase in omega-3 fatty acids. An adequate intake of omega-3 fatty acids results in anti-inflammatory and immunomodulatory effects that are protective against inflammatory tissue damage and capillary permeability. In addition, adults on Omegaven® seem to display improved immunological resistance. Omegaven® may also reduce the risk of thrombosis and increase microvascular perfusion due to its anti-aggregatory and vasodilatory effects.

In Europe and Asia, parenteral omega-3 fatty acids have been used in the following adult patient populations:

1. post traumatic and post surgical patients
2. patients experiencing early stages of sepsis/SIRS
3. patients at risk of hyperinflammatory processes
4. patients with inflammatory bowel disease (Crohn's disease, ulcerative colitis)
5. patients with inflammatory skin diseases (psoriasis, atopic eczema)

The dosing used in these patients was 0.1 (1ml) to a maximum of 0.2 g (2ml) /kg body weight. The infusion rate used did not exceed 0.5ml/kg/body weight/hour. Since it was intended to be infused in combination with conventional fat emulsions, the total fat intake was limited to 10-20% as fish oil. The duration of administration did not exceed 4 weeks.

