PNAC is a potentially fatal disorder, and the consequences are heinous if the process cannot be reversed. In Omegaven® we have an agent that is potentially life saving, and its use in hundreds of patients has shown little if any toxicity. After ongoing controlled trials of Omegaven® are completed, the agent will be evaluated for approval by the FDA. Until such time as FDA approval is granted, we will be unable to administer Omegaven® without requesting approval for compassionate use. The IRB granted approval for protocol 2009-1041, and this protocol will call for even stricter inclusion criteria. Therefore, we seek IRB approval for this study.

IV. Duration of Study

Once IRB approved, enrollment of subjects into this study will occur for up to 9 years. Subjects will receive Omegaven at a dose of up to 1 g/kg body weight/day until they no

longer require TPN or until their conjugated or direct bilirubin has normalized and their enteral lipid intake is sufficient to discontinue intravenous lipids.

A total study duration of 10 years is anticipated to complete the study (enrollment, analyses, and report writing).

V. Potential Benefits

The use of Omegaven® has the potential to benefit patients with PNAC by facilitating the resolution of cholestasis.

VI. Potential Risks of Omegaven® Treatment

Omegaven® has been studied in animal pre-clinical models as well as Phase I, II, III, and post marketing human trials in both Europe and Asia. Prolonged bleeding time and an inhibited platelet aggregation can occur. It should not be administered to patients known to be allergic to fish or egg protein.

Contraindications to Omegaven® include the following:

1. Impaired lipid metabolism
2. Severe hemorrhagic disorders
3. Unstable diabetes mellitus
4. Collapse and shock
5. Stroke/Embolism
6. Recent cardiac infarction
7. Undefined coma status

Side Effects:

Risks of Omegaven®

The infusion of Omegaven® can lead to a prolonged bleeding time and an inhibited platelet aggregation. In rare cases, patients may experience a fishy taste.

The administration of Omegaven® should be stopped or reduced if there is a marked increased in blood glucose levels during the Omegaven® infusion. Undesirable effects that are seen during the infusion of Omegaven® that may also occur with conventional fat emulsions (i.e., Liposyn® or Intralipid®) include:

1. Slight rise in body temperature
2. Heat sensation and/or cold sensation
3. Chills
4. Flushing or cyanosis

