Contact will occur by telephone unless subjects are seen in the clinic or are hospitalized. Applicable clinical records obtained at clinic visits and during hospitalizations such as H&Ps, labs, and medications can be used for research purposes.

Treatment with Investigational Drug

For the first two days of treatment, subjects will receive Omegaven® at 0.5 g/kg per day to assess tolerance and will progress to a maintenance dosage range of 0.8 to 1.2 g/kg/day over 12 hours at an infusion rate approximating 1 g/kg/12 hours (10 ml/kg/12 hours). The 12-hour infusion time will be used to minimize waste because of Centers for Disease Control and Prevention requirements that source containers of lipid emulsion be changed every 12 hours. Dosing is based on previously described dosing of fish-oil emulsions as monotherapy noted within the literature (8). Omegaven® will be infused intravenously through either a central or peripheral catheter in conjunction with other parenteral nutrition containing dextrose and amino acids. Omegaven® is isotonic. It is compatible with parenteral nutrition solutions and may be co-infused via y-site.

While hospitalized, serum triglyceride levels will be monitored weekly to insure that triglyceride concentrations do not exceed 1000 mg/dl during the infusion of fat emulsion. During hospitalization, coagulation studies will also be conducted weekly. PT and PTT will be conducted at baseline and then monthly. Other laboratory tests will be conducted to monitor for blood glucose metabolism, electrolyte and fluid balance and liver and kidney function in accordance with current institutional standards for monitoring hyperalimentation. Thromboelastography (prefer with platelet mapping) will be obtained at baseline and approximately 10 days prior to scheduled surgery to assess platelet aggregation dysfunction.

Urine pregnancy tests will be performed at baseline and monthly thereafter for females of child-bearing potential.

The patient will be observed for signs of metabolic overload and other adverse events. Adverse events will be documented by the study staff and may be used as a rationale for dosage adjustments of the study drug.

Study Drug Administration

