The DSMB chair (or designee) will be asked to review SAE reports within 7 days after initial receipt of the information by the investigator(s), to review the PIs assignment of SAEs as related or unrelated to treatment, to confirm the grading of any toxicities and assure that they do not meet stopping criteria.

A safety analysis will be performed after approximately 5 patients have received 4 weeks of treatment or, if enrollment begins slowly, 12 months after the first patient is enrolled. Safety data will be shared with the Data and Safety Monitoring Board (DSMB). There will be no further enrollment until the DSMB makes recommendations. An investigator in this study may not be a member of the DSMB. Members of the DSMB will receive safety data approximately every 2 to 3 months for review. Safety assessments will consist of vital signs, AEs, and laboratory evaluations. A cumulative listing of patient withdrawals, dose adjustments, and serious adverse events (SAEs) will also be reviewed. DSMB members will be notified of all SAEs reported expeditiously to regulatory authorities.

Study Monitoring

The Translational Research Trials Office (TRTO) will act as the independent monitor for the study. Routine monitoring visits shall occur one or more times during the period after study initiation but before study closeout. Guidelines for scheduling monitoring visits shall be determined according to the development, complexity of the study, the rate of subject accrual and other factors. Monitoring visits are conducted for routine monitoring only and are intended to ensure that the protocol and applicable regulatory requirements are being followed, that subjects' rights and safety are protected, and to confirm data integrity and quality.

XII. Adverse Events

An adverse event (AE) is any untoward medical occurrence in a patient participating in this trial. An adverse event can be an unfavorable and/or unintended sign (including an abnormal laboratory finding), symptom, syndrome or disease associated with or occurring during the use of an investigational product whether or not considered related to the investigational product.

A serious adverse event (SAE) is one that:

1. results in death
2. is life threatening
3. requires an inpatient hospitalization or prolonged a hospitalization
4. is disabling

5. is a congenital anomaly/birth defect

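### The protocol caps Omegaven at 1 g/kg/day in Sections II and IV but directs maintenance at up to 1.2 g/kg/day in Section IX.F

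*Combined protocol and SAP*

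**What the plan says.** Three places in the combined protocol and SAP give the Omegaven dose.

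- **Section II, Purpose of Study.** The aim asks whether cholestasis can be reversed if Omegaven "at a dose of up to 1 g/kg body weight/day is substituted for a soy-based intravenous lipid product".
- **Section IV, Duration of Study.** This is worded as an instruction: "Subjects will receive Omegaven at a dose of up to 1 g/kg body weight/day". The sentence goes on to say when treatment ends.
- **Section IX.F, Treatment with Investigational Drug.** The starting dose is given first: "For the first two days of treatment, subjects will receive Omegaven® at 0.5 g/kg per day to assess tolerance". Subjects then "will progress to a maintenance dosage range of 0.8 to 1.2 g/kg/day over 12 hours", with the infusion "at an infusion rate approximating 1 g/kg/12 hours (10 ml/kg/12 hours").

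Section XI (Study Monitoring) says that monitoring visits are "intended to ensure that the protocol and applicable regulatory requirements are being followed".

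**The concern.** Sections II and IV use the language of a ceiling. Section IX.F sets a planned maintenance range whose upper part lies above that ceiling. All three concern the same drug, the same subjects and the same unit, so a subject maintained at 1.1 g/kg/day would comply with IX.F and breach IV.

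The quantity in question is the maximum dose of an investigational drug in a population that starts at one month of age. Three things depend on it:

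- **Protocol compliance.** For any dose above 1.0 and up to 1.2 g/kg/day, a monitor checking adherence has two limits and no rule for choosing between them.
- **Administration and oversight.** Section IX.F passes administration from the hospital pharmacy to the home care pharmacy and/or the family. Section XI has the DSMB review a cumulative listing of dose adjustments. Both need one reference dose.
- **Reporting.** The dose named in the aim is not the dose that the treatment section allows, so a report could misdescribe what was tested.

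**Working it through.** **Inputs**

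| Quantity | Value | Source |
|---|---|---|
| Dose in the aim | at most 1 g/kg/day | Section II |
| Dose subjects are to receive | at most 1 g/kg/day | Section IV |
| Maintenance range | 0.8 to 1.2 g/kg/day, over 12 h | Section IX.F |
| Infusion rate | about 1 g/kg per 12 h, given as 10 ml/kg per 12 h | Section IX.F |
| Emulsion concentration | 0.1 g per ml | Section III, from "The dosing used in these patients was 0.1 (1ml) to a maximum of 0.2 g (2ml) /kg body weight" |

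**Step 1: reproduce the protocol's own conversion.** Volume = dose / concentration = 1 g/kg / 0.1 g/ml = 10 ml/kg. This agrees with the 10 ml/kg in Section IX.F.

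**Step 2: compare the top of the range with the ceiling.**

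- Excess: 1.2 − 1.0 = 0.2 g/kg/day
- Relative excess: 1.2 / 1.0 − 1 = 20%
- As volume: 1.2 / 0.1 = 12 ml/kg, against 10 ml/kg

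**Step 3: find how much of the range is in dispute.** The range is 1.2 − 0.8 = 0.4 g/kg/day wide and the part above the ceiling is 0.2, so 0.2 / 0.4 = one half. This is a share of the permitted range, not of subjects. The documents give no expected dose distribution.

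**Step 4: check the link to rate and duration.** The stated rate is 1/12 = 0.083 g/kg/h. At exactly that rate, 1.2 g/kg takes 1.2 / (1/12) = 14.4 h. To finish in 12 h it needs 1.2 / 12 = 0.100 g/kg/h. The rate is worded as approximate, so this is not a second contradiction. It shows only that the rate and the 12-hour duration have to be read together with whichever dose text is kept.

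**Step 5: look for text that reconciles the two.**

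- Inclusion criterion 4 (Section IX.A) also uses 1.2 g/kg/day, but for soy-based lipid before entry, not for Omegaven.
- The Dose Reduction text in IX.F only lowers the dose, for triglycerides above 1000 mg/dL.
- Section IX.F says in general terms that adverse events may justify dosage adjustments. That does not raise a stated ceiling.
- No supplied passage calls 1 g/kg/day nominal, gives a tolerance around it, or sets an order of precedence between sections.

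**The case against.** The best defence is that 1 g/kg/day was always a nominal dose. Section IX.F is the only section devoted to treatment and the only one that gives starting dose, maintenance range, rate, duration and route. Its range is symmetric around 1 and stands beside a rate worded as approximating 1 g/kg. On this reading IX.F supplies the tolerance, and II and IV are loose summaries. Section II states a research question and does not direct dosing. The sentence in Section IV appears under a heading about duration and mainly defines when treatment stops. Staff working from the treatment section would find one explicit range. The monitoring statement in Section XI is general and mentions neither dose checks nor deviation criteria.

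Much of this is fair. The nominal reading is plausible, Section II is weaker evidence of a limit than Section IV, and the consequence for monitoring is inferred from the wording and not shown in operation. None of it removes the conflict. The words used set an upper bound, not a target; they occur twice; and in Section IV they say what subjects will be given. A reader cannot tell from the document that IX.F is meant to override them.

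**Conclusion.** The contradiction stands on the current text. Section IX.F permits maintenance doses up to 0.2 g/kg/day (20%) above the limit in Section IV and the dose described in the Section II aim. Doses of 0.8 to 1.0 g/kg/day are consistent throughout; the conflict is confined to doses above 1.0 and up to 1.2.

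This is a matter the sponsor should correct, not a flaw in the statistical design. The sample size, alpha, power and analysed population do not depend on it. The conclusion rests on reading the wording in II and IV as a maximum, which is its ordinary meaning. The number of subjects affected is unknown. The consent form was not among the documents and could not be compared. No view is taken on which dose is right.

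**What to change.** The sponsor should reconcile Sections II, IV and IX.F so that the same dose limit or range appears in all three, and should state whether 1 g/kg/day is a ceiling or a nominal value. The approximate infusion rate and the 12-hour duration in IX.F should be checked against the reconciled text so that dose, rate and duration agree. The choice of figure belongs to the sponsor. The cost is amendment wording only, with no change to the design, sample size or analysis.
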